dose of dronabinol (20 mg, 35 mg, 50 mg). In this single-blinded phase, the subject will not know which dose he/she is receiving. The protocol for the study visit will be identical. As there are three levels of drug exposures, there are 6 possible orders in which subjects can receive the three doses (e.g. high, medium, low; medium, low, high; etc). Subjects will be randomly assigned to one of the 6 possible orders according to a randomization schedule generated by the study staff using a random number generator and computer program. In order for a complete washout of effects, and to minimize the effect of repeat testing for the neuropsychology tasks, study visits must be at least 1 week apart. See below for schematic:

Subjects who participated in Phase 1 or 2 will be eligible for Phase 3, but enrollment in Phase 1 or 2 is not a requirement for Phase 3. Therefore, new subjects who have not completed Phase 1 or 2 will also be eligible for Phase 3.

Driving Simulation: During this phase, we will use a computer-programmed driving simulator to assess motor coordination of the participants. The simulation will be programmed in STISIM on the computer and will be administered by a trained research coordinator. Subjects will be trained on this task during the screening task during the screening visit and given a refresher training on the task before testing. The task is performed on a laptop with the use of the keyboard, a joystick, and a foot pedal. Participants perform tasks where they must center an object on the screen using the joystick, in addition to identifying numbers with the tap of the foot pedal.

Participants: 60 healthy, weekly or greater MJ users, aged 18-55, will be enrolled. Participants must test positive for cannabis, and negative for other addictive drugs and have no serious unstable medical illness to participate in the Phase III (See Participant Selection Section).

Biostatistical Analysis

Data variables collected for study

Standardized questionnaires, assessing drug use, personality characteristics, and anxiety will be collected, as well as task data and neural signaling data from the fNIRS testing sessions.

All data will be collected and managed using REDCap electronic data capture tools (Harris 2009) hosted with Partners HealthCare.

Vanderbilt University, with collaboration from a consortium of institutional partners, has developed a software toolset and workflow methodology for electronic collection and management of research and clinical trial data. REDCap (Research Electronic Data Capture) data collection projects rely on a thorough study-specific data dictionary defined in an iterative self-documenting process by all members of the research team with planning assistance from Partners HealthCare Research Computing, Enterprise Research Infrastructure & Services (ERIS) group. The REDCap Survey is a powerful tool for building and managing online surveys. The research team can create and design surveys in a web browser and engage potential respondents using a variety of notification methods. Both REDCap and REDCap Survey systems provide secure, HIPAA compliant, web-based applications that are flexible enough to be used for a variety of types of research, provide an intuitive interface for users to enter data and have real time validation rules (with automated data type and range checks) at the time of entry.

fNIRS Data Analysis

The instrument will acquire raw data for each detector at ~40 kHz. The individual source signals then will be obtained with a digital bandpass filter – for example, a discrete Fourier transform or an infinite-impulse-response filter. The individual source signals will be separated off-line with an infinite-impulse-response filter with a 50 Hz band pass frequency. Next, the time series pairs from each detector will be converted from wavelength (absorption) to relative concentrations (of oxy-/deoxy-hemoglobin). This will be done with the modified Beer-Lambert Law and the absorption coefficients of oxy- and deoxy-hemoglobin (HbO and Hb, respectively) [34]. (The near-IR wavelengths are chosen because oxy-/deoxy-Hb are the predominant absorbers in the tissue at these wavelengths.) The result will be an oxy-Hb and deoxy-Hb timeseries associated with each source-detector pair.

For each stimulation run, each smoothed oxy-/deoxy-hemoglobin time series will be examined for periodic amplitude fluctuations. Expected fluctuations include heart rate (~1Hz), breathing and/or “v-waves” (~0.1Hz), as well as any fluctuations induced by the experimental paradigm. If the former sources of noise are substantial, an attempt will be made to filter out these fluctuations (in Fourier space). Any analysis of filtered data will be compared to an analysis of the corresponding non-filtered data. The oxy-hemoglobin portion of the experimentally induced changes are expected to be 4-9 sec out of phase with the paradigm onsets and offsets (as seen in fMRI work as well as in prior optical recordings).

Study endpoints

As this is not a clinical trial, we will collect data from up to 20 participants in Phase 0, up to 100 participants in Phase I, up to 200 in Phase II and up to 60 in Phase III in order to investigate whether we can determine the brain signals involved in marijuana intoxication. Given that the planned studies are pilot in nature, and that we will be using

a recently developed instrument, the relevant effect sizes are unknown and therefore power analysis cannot be adequately performed. However, some estimates can be made. The biological basis for the signals measured by the optical technique is the same as the basis for fMRI and PET scanning. In a similar study using PET (*R.J. Mathew et al. / Psychiatry Research: Neuroimaging 116 (2002) 173–185*), indices of rCBF, intoxication and physiology were measured at baseline and 30, 60, 90 and 120 min. after an intravenous infusion of 0.15 or 0.25 mg of THC, or placebo. Significant increases were seen in global perfusion and in the frontal, insular and anterior cingulate regions. This study had a sample size of 47 subjects in each group. Therefore, we will collect data in 100 participants, as this is a conservative estimate of the power we will need to detect an effect.

Statistical methods

Statistical analysis of data will be performed using SPSS, STATA, and fNIRS analysis software.

Risks and Discomforts

Potential adverse events due to dronabinol:

Risks: Dronabinol-induced sympathomimetic activity may result in tachycardia and/or conjunctival injection. Its effects on blood pressure are inconsistent, but occasional subjects have experienced orthostatic hypotension and/or syncope upon abrupt standing. Dronabinol also demonstrates reversible effects on appetite, mood, cognition, memory, and perception. These phenomena appear to be dose-related, increasing in frequency with higher dosages, and subject to inter-patient variability.

After oral administration, dronabinol has an onset of action of approximately 0.5 to 1 hours and peak effect at 2 to 4 hours. Duration of action for psychoactive effects is 4 to 6 hours.

Tachyphylaxis and tolerance develop to some of the pharmacologic effects of dronabinol and other cannabinoids with chronic use, suggesting an indirect effect on sympathetic neurons. In a study of the pharmacodynamics of chronic dronabinol exposure, healthy male volunteers (N = 12) received 210 mg/day dronabinol, administered orally in divided doses, for 16 days. An initial tachycardia induced by dronabinol was replaced successively by normal sinus rhythm and then bradycardia. A decrease in supine blood pressure, made worse by standing, was also observed initially. These volunteers developed tolerance to the cardiovascular and subjective adverse CNS effects of dronabinol within 12 days of treatment initiation.

In the clinical trials, the majority of patients were treated with 5 mg/day MARINOL Capsules, although the dosages ranged from 2.5 to 20 mg/day.

Minimization: If there are any concerns about a subject in need of clinical attention, the PI will be made aware of the issue immediately and will consult with appropriate medical personnel (co-investigator: A. [name], or another study physician) to determine appropriate steps. The PI and medically trained co-investigators will assess the needs of the subject and offer the subject either prompt treatment or medical referral, whichever is appropriate for the situation. There is a licensed physician/registered nurse on site 40 hours per week, and other MGH resources can be used as necessary.

Potential adverse events due to ethanol:

Risks: At low to moderate doses, ethanol can produce behavioral intoxication and physiological changes (feeling intoxicated, high, euphoric, dizzy, giddy, tired and lightheaded; increased heart rate, slurred speech, and slowed reaction time). These effects will not be novel to our subjects who will have experience drinking. The amount of alcohol administered is similar to that experienced by casual users of this drug and is fairly low for moderate to heavy users.

Minimization: Participants will not be required to perform any physical tasks while intoxicated. Drinking alcohol under controlled laboratory conditions is unlikely to change current use patterns or cause addiction. If there are any concerns about a subject in need of clinical attention, the PI will be made aware of the issue immediately and will consult with appropriate medical personnel (co-investigator: A. [name], or another study physician) to determine appropriate steps. These investigators will handle any adverse reaction (physical or psychological) to the drug administration.

Psychosocial risks

Risks: There is no social risk associated with participation in this study. There are few legal risks to the participants associated with these paradigms. Cannabis use is decriminalized in Massachusetts, thus there is no legal risk to self-report of regular cannabis use. However, a possible risk is that subjects may come up positive on a workplace drug screen if they take part in this study.

Minimization: We will provide subjects with documentation that describes the study procedures, and states that participation in this study will affect any drug screen results.

Confidentiality and Loss of Privacy

Risks: The risk of loss of privacy is judged to be minimal.

Minimization: Confidentiality will be maintained by numerically coding all data and by keeping all data in locked file drawers and deidentified data in password protected databases. Subject information will be accessible only to research staff. Information about study participants will not leave our institution in any form that would identify individual subjects.

fNIRS Risks

Risks: fNIRS is a minimal risk procedure. fNIRS assess the brain's hemodynamic response by employing optical properties of light. Unlike fMRI, fNIRS only collects data ~3 cm into the cortex. fNIRS employs non-ionizing near-infrared light, so no cancerogeneous or genetic effects are possible. The light intensity is kept well below

safety limits to avoid the risk of thermal damages. No cumulative harmful effects of such light exposure to the forehead are known, and fNIRS measurements are commonly applied repeatedly or in a continuous manner for monitoring purposes.

Minimization: Subjects who may become uncomfortable during the fNIRS procedure will be able to converse with the experimenter and will be able to communicate any desire or need to stop the procedure. All efforts will be made to make the subjects as comfortable as possible. A member of the study staff will explain the procedure thoroughly to the subject, allowing for maximal understanding and comfort. The testing can be stopped at any time at the subjects' request. A qualified physician/nurse will be on site or reachable by pager during all study visits in the unlikely event that an adverse event occurs.

The likelihood for the need for medical or professional intervention for a participant in this study is reduced by the protocol enrollment criteria that specify that we will enroll only medically stable, healthy adults to the study. Subjects will be asked to report adverse events at any time by calling study staff and will be asked to report adverse events at each study visit.

Risks of blood draws

Risks: The discomfort associated with removing (by catheter from a vein) is a slight pinch or pin prick when the sterile needle enters the skin. The risks include mild discomfort and/or a black and blue mark at the site of puncture. Less common risks include a small blood clot, infection or bleeding at the puncture site, and on rare occasions fainting during the procedure. There will be only a small amount of blood drawn (about 1 mL) each time.

Minimization: Blood draws will be taken by trained nursing staff at the Translational and Clinical Research Center or Center for Addiction Medicine at Massachusetts General Hospital. The total amount of blood drawn will not exceed 5 ccs per draw or 45 ccs per study day. If there are any concerns about a subject in need of clinical attention, the PI will be made aware of the issue immediately and will consult with appropriate medical personnel to determine appropriate steps.

Potential Benefits

There is no direct benefit to participating in this research. Some participants may find that talking about marijuana use increases their awareness of any issues related to drug use. Any participant who asks about treatment will be provided information regarding local drug treatment programs.

Information developed from this study may help researchers in the future. Specifically it is expected that this study will provide valuable information to the field of acute marijuana effects on the brain.

MONITORING AND QUALITY ASSURANCE

All participants will have contact information for the principal investigator and the study coordinator if they have questions at any time. [name] is responsible for the overall management of the study and will maintain regular communication with all of the study staff. The PI will meet weekly with all study investigators to review the details of data acquisition and analysis as well as any minor problems. In the event of any minor or significant adverse event the PI will be contacted immediately. The PI is responsible for the generation of summary reports to the Partners HRC and to NIH, documenting this process and outcome.

Serious adverse events are not expected as a result of the study procedures. Should one occur, it will be reported by telephone or email by the principal investigator to the Partners IRB according to current PHRC Adverse Event Reporting Policy (version dated: March 13, 2007). All adverse events (if not serious) will be reported in writing to the Partner's Human Research Committee. All information regarding experimental subjects will be kept in the offices of the Principal Investigator. All data will be identified by a unique code number.

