Study Drug and Dosing: Participants will be given up to 50mg of MARINOL® (dronabinol) in all phases except Phase IIA and IIB, in which they will be given up to 80mg of dronabinol. Dronabinol is an FDA-approved synthetic form of cannabis that is used to treat loss of appetite that causes weight loss in people with AIDS. Dronabinol contains synthetic THC, the principle psychoactive drug in marijuana. The study physician/nurse and co-investigator, Dr. [name] MD, as well as physicians/nurse on study staff at the Center for Addiction Medicine, will be responsible for administering the drug.

Dronabinol will be dosed at up to 80mg. The rationale for this dose is based on several factors. The study will be conducted in regular cannabis users who present at their first study visit with a positive urine screen for THC metabolites. Chronic cannabis use is associated with significant tachyphylaxis and tolerance to pharmacologic effects of THC and other cannabinoids. In healthy males who received 210 mg/day dronabinol for 16 days, tolerance developed to the CNS effects of dronabinol (including the euphoric 'high' effect) within 12 days. At doses of 5 mg/day for appetite stimulation in 139 patients, only 18% experienced any CNS effect (feeling high, dizziness, confusion, somnolence). These CNS effects are the target symptoms we wish to assess in study participants. Because of tolerance, the rate of CNS effects is expected to be lower in our study population than in non-cannabis users who participated in marinol studies for anti-emetic and appetite stimulation indications.

Marinol was evaluated in 454 patients with cancer at doses up to 40 mg/day. At doses greater than 0.175 mg/kg approximately 58% reported feeling 'high'. The starting recommended antiemetic dose is 15-20mg/day, noting that dosage may be escalated during a chemotherapy cycle or at subsequent cycles based upon initial results.

For appetite stimulation, the recommended dose range is up to 20 mg/day, and at this dose approximately half of patients tested have reported CNS symptoms targeted in this study (feeling high, dizziness, confusion, somnolence).

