Thus, we will dose at up to 80mg and will assess for CNS symptoms frequently during the study visit. The exact dronabinol dose will be clinically determined by a study physician. The dose will be designed to minimize adverse psychologic and physiologic effects of dronabinol and will be primarily based on the degree of tolerance expected (based on dose and frequency of cannabis use), self report of degree of intoxication experienced with each use, and any regular or prior negative psychological reactions to cannabis use or binges. This is an inexact determination as potency of cannabis used is almost never known. Other factors that will be considered when determining dose are height, weight, BMI, and baseline blood pressure. For example: Heavy daily cannabis users will generally receive 80mg. Daily cannabis users who use 1/2-1 gram per day and who weigh over approximately 140 pounds will generally receive 50mg, while those who use less than half a gram per day, use less than daily or who weigh less than 100 pounds will receive between 30 and 45 mg based on the physician's best judgment.

Urine Drug Screen: Before study procedures are initiated, we will perform a qualitative urine drug screen (Multi Drug 6 Panel Urine Test; Medimpex United Inc., Bensalem, PA) that will test for marijuana, amphetamines, methamphetamines, cocaine, and opiates. These rapid tests are simple, can be done at home, and are CLIA-waived. The test will be administered by a trained research coordinator.

Urine Pregnancy: Before study procedures are initiated, we will perform a qualitative urine pregnancy test for females. The test will be administered by a trained research coordinator.

[figure not shown]
Overview of Procedures for Each Phase:

Phase 0: Participants will come to the MGH Martinos Center the day of their study visit. They will meet with a study doctor and sign the consent form. Those who are eligible after the telephone screen will then undergo one fNIRS testing session. The testing session will take approximately one hour to complete. The testing procedure only consists of the n-back task (see "Cognitive Tasks during FNIRS testing" for description of the task). There is no drug administration in Phase 0.

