participants will also provide a urine sample which will be tested for drugs and pregnancy (if applicable) to ensure participants are positive for THC. Participants are trained on the driving simulator computer tasks. If participants are determined to be eligible, they will be scheduled for the following two visits. In a double-blind, placebo-controlled, random order cross-over study of single dose THC (dronabinol) at physician determined doses of 10-80mg, participants will receive THC capsules or identical placebo on two separate study visits, randomized for order. The MGH research pharmacy will generate a blinded randomization code for order of dosing and will dispense blinded drug in the dose ordered and identical placebo for use on separate study days. In order for a complete washout of effects, and to minimize the effect of repeat testing for the neuropsychology tasks, study visits must be at least 1 week apart. On each study day, participants will have a light standardized breakfast after overnight fast and sleep. They will be asked not to deviate from normal behaviors (e.g. if they drink caffeinated beverages or smoke cigarettes in the mornings, they will be asked to do so on the study day so that no symptoms of caffeine or nicotine withdrawal will appear during the scanning period. On each study day, participants will undergo baseline fNIRS testing (see above “Cognitive Tasks during FNIRS testing”), substance use history interview (timeline follow back), two sets of baseline vital signs, a driving simulator computer task refresher, and several questionnaires (HADS, URGE, PSQI, CWS). Dronabinol or placebo will be administered once morning procedures are complete, after which point heart rate, blood pressure, and responses to DEQ and BAES questionnaires will be monitored at 20 minute intervals. The second fNIRS session will be conducted at approximately 90 minutes post dose, followed by driving simulator computer tasks. A field test of sobriety will be conducted immediately following the second fNIRS assessment. The third fNIRS session will be conducted at approximately 220 minutes post dose, prior to participant discharge. See Below for schematic:

Subjects who participated in Phase 1 will be eligible for Phase 2, but enrollment in Phase 1 is not a requirement for Phase 2. Therefore, new subjects who have not completed Phase 1 will also be eligible for Phase 2.

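### The dronabinol dosing text places heavy daily users in Phase 1 under both a 50 mg cap and a usual dose of 80 mg, and heavy daily users under 100 lb in two dose tiers

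*Protocol*

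**What the plan says.** Five statements in section X of the protocol bear on dose.

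- **Limits by phase (Study Drug and Dosing, opening sentence).** "Participants will be given up to 50mg of MARINOL" applies "in all phases except Phase IIA and IIB, in which they will be given up to 80mg of dronabinol".
- **Maximum with no phase named.** The next paragraph opens "Dronabinol will be dosed at up to 80mg", and the text that follows the dose rationale repeats it: "Thus, we will dose at up to 80mg and will assess for CNS symptoms frequently during the study visit".
- **Tier guide, also with no phase named.** A study physician sets the dose, and examples follow. The top tier is "Heavy daily cannabis users will generally receive 80mg". The middle tier is generally 50 mg, for daily use of 1/2-1 g and a weight above roughly 140 lb. The lowest tier covers use under half a gram a day and those who "use less than daily or who weigh less than 100 pounds will receive between 30 and 45 mg", subject to the physician's judgment.
- **Phase 2A.** The crossover uses "physician determined doses of 10-80mg". Phase 2B takes its dronabinol administration from Phase 2A.
- **Phase 3.** Each participant receives a low, a medium and a high dose over three sessions in random order ("dose of dronabinol (20 mg, 35 mg, 50 mg").

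The Phase 1 procedures say only that a dose of dronabinol is given. They state no figure.

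**The concern.** A maximum dose of an intoxicating drug should have one reading in each phase. If two statements in the same section give different answers for the same person, staff can follow the protocol and still exceed a limit stated elsewhere in it. A monitor also could not say whether a deviation had occurred. This is a matter of participant safety and protocol compliance. The test is whether any eligible participant meets two rules that cannot both be followed, as opposed to rules that are merely broad or incomplete.

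**Working it through.** The documents state no figure to reproduce. The check applies each dosing rule to types of participant whom each phase can enrol.

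**1. Heavy daily user, Phase 1**

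- Eligibility: Phase 1 plans 100 adults, about half of them heavy users, defined there as using more than once a week. Daily users are a subset of that group.
- Rule A (limits by phase): Phase 1 is neither 2A nor 2B, so at most 50 mg.
- Rule B (top tier, no phase named): generally 80 mg.
- Difference: 80 - 50 = 30 mg; 30/50 = 60% above the cap.
- The Phase 1 procedures give no dose, so they do not decide between A and B.

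**2. Heavy daily user under 100 lb, Phase 2A**

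- Eligibility: in Participant Selection, the requirement to weigh more than 100 lb is an additional criterion for Phase 2B only. Phase 2A has no minimum weight.
- Top tier: 80 mg, on use pattern.
- Lowest tier: 30-45 mg, on weight. The conditions are joined by "or", so weight alone is enough.
- Difference between the tiers: 80 - 45 = 35 mg to 80 - 30 = 50 mg.
- Both tiers lie inside 10-80 mg, so the Phase 2A range does not choose between them.

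**3. Low end of the Phase 2A range**

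- The tiers give 30-45, 50 and 80 mg. All lie inside 10-80 mg, so no tier breaches the range.
- None leads to 10-29 mg, so the 10 mg floor is unexplained. This is a gap and not a conflict.

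**4. Phase 3**

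- The assigned doses of 20, 35 and 50 mg are all within the 50 mg cap.
- If the guide also applied here, a less-than-daily user (admitted, since Phase 3 takes weekly or greater users) would receive two of three doses outside 30-45 mg: 30 - 20 = 10 mg below and 50 - 45 = 5 mg above. The text does not say that the guide is set aside.

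**The case against.** The best defence is that the opening sentence separates 50 and 80 mg by phase, and that the later 80 mg statements only explain the study-wide maximum. The tiers are introduced as examples, two of the three are qualified as general practice, and the physician decides. Much of this stands, and it disposes of several stronger readings that a reader might infer:

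- **That 50 mg and 80 mg contradict each other as caps.** They do not, because they are assigned to different phases. The conflict arises only from the later statements that name no phase.
- **That 10-80 mg contradicts 30-45 mg.** The first range contains the second.
- **That a daily user of 1/2-1 g weighing 100-140 lb, who fits no tier, is left without a rule.** The list is of examples, and the physician's determination covers that person.
- **That Phase 3 breaks the guide.** Its doses are assigned by protocol to study dose effects, and the specific text would ordinarily govern. Only the silence on scope remains.
- **That the conflict affects dosing with ethanol.** The upper limit for Phase 2B is 80 mg throughout, and its weight criterion excludes the tier overlap.
- **That the Phase 1 and Phase 3 points change the meaning of the SAP's THC term.** The SAP covers Phases 2A and 2B only.

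The defence does not remove the two conflicts. Calling the tiers examples does not say which phases they serve, and physician judgment does not tell the physician which of two stated limits binds in Phase 1. Nor does it say whether use pattern or weight takes precedence in the guide.

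**Conclusion.** The dosing text gives incompatible instructions for two identifiable groups: heavy daily users in Phase 1 (usual dose 30 mg, or 60%, above the stated cap) and heavy daily users under 100 lb in Phase 2A (two tiers 35 to 50 mg apart). The unexplained 10-29 mg and the guide's silence on Phase 3 are secondary questions of scope.

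The conclusion assumes that statements naming no phase are read as written, and that daily users fall within Phase 1's heavy group, as its definition allows. The guide does not define heavy daily use, and the documents do not say how many participants fall in either group, so the number affected is unknown. It is some part of the roughly 50 heavy users planned for Phase 1, and possibly few people in Phase 2A.

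The eightfold width of the Phase 2A range (80/10) is not evidence of contradiction, since it only measures the latitude given to the physician. The point should be corrected because it concerns a stated maximum exposure, but it is an inconsistency of wording and not a flaw in the design.

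**What to change.** Reconcile the opening limits, the later 80 mg statements and the tier guide in Study Drug and Dosing with the Phase 2A range and the Phase 3 doses, so that:

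1. each phase that gives dronabinol has one stated dose or dose range;
2. the tier guide names the phases to which it applies, and says whether it applies to Phase 3;
3. no participant can fall in two tiers;
4. the relation between the guide and the low end of the Phase 2A range is stated.

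Which figures and which order of precedence are right is for the sponsor and investigator. The cost is protocol wording, with no change to design or analysis. As an optional addition, the SAP could include one descriptive table of delivered dose for Phases 2A and 2B. That would help readers interpret the THC contrast, but the inconsistency does not require it.
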